2 STATISTICAL ANALYSES

2.1 GENERAL CONSIDERATIONS

In general, continuous data will be summarized using the number of observations available, mean, standard deviation (SD), median, Q1, Q3, minimum, and maximum. Categorical and ordinal data will be summarized using the count and percentage of participants.

The baseline value is defined as the last available value before the first dose of double-blind IMP. For participants randomized but not treated, the baseline value is defined as the last available value before randomization.

Unless otherwise specified, analyses will be performed by intervention group and overall, for baseline and demographics characteristics.

The intervention groups will be presented as follows:

- Period A: SAR442970 150mg q2w and Placebo.
- Period B and Period C: SAR442970 150 mg q2w/SAR442970 150 mg q2w, Placebo/SAR442970 150 mg q2w and overall unless otherwise specified.

Observation period

The observation period will be divided into the following segments:

The pre-treatment period is defined as the period up to first blinded IMP administration.

Period A:

- The **treatment-emergent (TE) period of Period A** is defined as the period from the first blinded IMP administration to the last blinded IMP administration + 75 days or the first open-label IMP administration, whichever occurs earlier. The TE period of Period A includes the following 2 sub-periods:
 - The **on-treatment period of Period A** is defined as the period from the first blinded IMP administration to the last blinded administration of the IMP + 14 days, or the first open-label IMP administration, whichever occurs earlier.
 - The **residual treatment period of Period A** is defined as the period after the end of the on-treatment period of Period A to the end of the TE period of Period A.

Period B:

- The **treatment-emergent (TE) period of Period B** is defined as the period from the first open-label IMP administration to the last open-label IMP administration + 75 days. The TE period of Period B includes the following 2 sub-periods:
 - The **on-treatment period of Period B** is defined as the period from the first open-label IMP administration to the last open-label administration of the IMP + 14 days.

- The **residual treatment period of Period B** is defined as the period after the end of the on-treatment period of Period B to the end of the TE period of Period B.

The post-treatment period is defined as the period after the end of the TE period of Period B, or after the end of TE period of Period A if the participant does not enter the Period B.

Any lesion that is treated with steroid injection, deroofing, or other local intervention, the lesion is considered present throughout the double-blind period and open-label period. Types of lesions include abscess, non-inflammatory nodule, inflammatory nodule, nondraining tunnel, draining tunnel, hypertrophic scar.

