#### ***9.2.6.2 Laboratory variables, vital signs, and electrocardiograms (ECGs)***

##### **Quantitative analyses**

When relevant, for laboratory variables, vital signs and ECG variables, descriptive statistics for results and changes from Baseline will be provided for each planned visit during the on-treatment period. These analyses will be performed using central measurements only for laboratory variables.

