1.1 STUDY DESIGN

This is a multinational, randomized, placebo-controlled, double-blind, Phase 2a proof-of-concept study. The purpose of this study is to evaluate the efficacy, safety, PK, biological effects of SAR442970 compare with placebo in adult participants with moderate to severe hidradenitis suppurativa (HS).

The study is composed of 3 parts: a double-blind, placebo-controlled period (Period A), followed by an open-label period (Period B), and then a safety Follow-up Period (Period C). After a screening period of 2 to 4 weeks, participants will receive SAR442970 150 mg or matching placebo Q2W at the Week 0 visit up to the Week 14 visit as part of Period A. Beginning at the Week 16 visit, all participants will receive SAR442970 150 mg Q2W up to the visit prior to the individual participant's end of treatment (EOT) visit as part of Period B. Period C will commence with the End of Treatment (EOT) visit and conclude with the End of Study (EOS) visit. For participants in the US, response will be assessed at the Week 20 visit (see definition of response in [Section 2.2.1](#)). Responders at Week 20 will continue in Period B to complete the 12-week open-label period. Non-responders at Week 20 will move directly to the safety follow-up period (Period C) with the Week 20 visit serving as their EOT visit.

Approximately 84 participants will be randomized in a 2:1 ratio to SAR442970 150 mg Q2W or matching placebo. Randomization will be stratified by HS treatment history (biologic and small molecule immunosuppressive-naïve or TNF-experienced) and Hurley stage (II or III). The recruitment target is approximatively 66 biologic and small molecule immunosuppressive-naïve and approximatively 18 TNF-experienced. Within the biologic and small molecule immunosuppressive-naïve subgroup, the number of participants with Hurley Stage III is not to exceed more than 50%. Within the biologic and small molecule TNF-experienced subgroup, the number of participants with Hurley Stage III is not to exceed more than 50%.

The primary analysis population is the biologic and small molecule immunosuppressive-naïve subgroup. Efficacy objectives and endpoints will be evaluated in an exploratory manner in the TNF-experienced subgroup.

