2.7.3 Additional safety assessments

2.7.3.1 Laboratory variables, vital signs, and electrocardiograms (ECGs)

The following laboratory variables, vital signs, and electrocardiogram (ECG) variables will be analyzed. They will be converted into standard international units.

- Hematology:
 - Red blood cells and platelets and coagulation: hemoglobin, hematocrit, red blood cell count, platelet count, mean corpuscular volume, mean corpuscular hemoglobin concentration, mean corpuscular hemoglobin and reticulocytes
 - White blood cells: white blood cell count, neutrophils, lymphocytes, monocytes, basophils, eosinophils
- Clinical chemistry:
 - Metabolism: fasting glucose, fasting total cholesterol, fasting triglycerides, fasting high-density lipoprotein, fasting low-density lipoprotein, fasting very low-density lipoprotein, total protein, albumin, creatine phosphokinase
 - Electrolytes: sodium, potassium

- Renal function: creatinine, creatinine clearance, blood urea nitrogen. Creatinine clearance will be derived with the equation of Cockcroft and Gault using weight assessed at the same visit as creatinine.
- Liver function: alanine aminotransferase (ALT)/ Serum glutamic-pyruvic transaminase, aspartate aminotransferase (AST)/ Serum glutamic-oxaloacetic transaminase, alkaline phosphatase, total and direct bilirubin
- Vital signs: heart rate (beats per minute), systolic and diastolic blood pressure (mmHg) in sitting or semi-supine position, weight (kg), respiratory rate, temperature
- ECG variables: heart rate, PR, QRS, QT, and corrected QTcF (according to Fridericia).

Data below the lower limit of quantitation/detection limit (LLOQ) will be replaced by half of the LLOQ, data above the upper limit of quantification will be replaced by ULOQ value.

Quantitative analyses

For laboratory variables, vital signs, and ECG variables above, descriptive statistics for results and changes from baseline will be provided for each analysis window during the on-treatment period. These analyses will be performed using central measurements only (when available) for laboratory variables.

For all parameters, mean changes from baseline with the corresponding standard error will be plotted over time.

Analyses according to PCSA

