A measurement (scheduled or unscheduled) will be used if it is available and measurement date is within the analysis window.

After applying these time windows, if multiple assessments are associated to the same time point, the closest from the targeted study day will be used. If the difference is a tie, the value after the targeted study day will be used. If multiple valid values exist within a same day, then the first value of the day will be selected. For procedures planned on Visit 2, if it is done on the same date as the first IMP injection but the performance time is missing, it will belong to the Visit 2 window.

If there is no measurement for a given parameter in an analysis window, data will be considered missing for the corresponding visit.

Table 12 - Analysis window definition for safety analysis

Analysis visits	Targeted study day ^a	Time window				
		Vital signs	Fasting lipid panel	Non-fasting laboratory tests	Urinalysis	12-lead ECG
Period A						
Screening	-28 to -14	<-14	<-14	<-14	<-14	<-14
Baseline	1	-14 - 1	-14 - 1	-14 - 1	-14 - 1	-14 - 1
Week 2	15	2 - 21	2 - 21	2 - 21	2 - 21	2 - 21
Week 4	29	22 - 35	22 - 35	22 - 35	22 - 35	22 - 35
Week 6	43	36 - 49	36 - 49	36 - 49	36 - 49	36 - 49
Week 8	57	50 - 63	50 - 63	50 - 63	50 - 63	50 - 63
Week 10	71	64 - 77	64 - 77	64 - 77	64 - 77	64 - 77
Week 12	85	78 - 91	78 - 91	78 - 91	78 - 91	78 - 91
Week 14	99	92 - 105	92 - 105	92 - 105	92 - 105	92 - 105
Week 16	113	106 - D ^b	106 - D ^b	106 - D ^b	106 - D ^b	106 - D ^b
Period B						
Week 18	15	2 - 21	2 - 21	2 - 21	2 - 21	2 - 21
Week 20	29	22 - 35	22 - 35	22 - 35	22 - 35	22 - 35
Week 22	43	36 - 49	36 - 49	36 - 49	36 - 49	36 - 49
Week 24	57	50 - 63	50 - 63	50 - 63	50 - 63	50 - 63
Week 26	71	64 - 77	64 - 77	64 - 77	64 - 77	64 - 77
Week 28	85	78 - 112	78 - 112	78 - 112	78 - 112	78 - 112
Week 36	141	>112	>112	>112	>112	>112

a Day 1 in Period A is the day of the first blinded IMP administration (or the day of randomization for participant not exposed).

Day 1 in Period B is the day of the first open-label IMP administration.

b Last window in Period A is the 1st dose of open-label IMP administration.

Table 13 - Analysis window definition for efficacy endpoints

Analysis visit	Targeted study day ^a	Time windows			
		HS clinical parameters	Dermatology Life Quality Index	Hidradenitis Suppurativa Quality of Life	
Period A					
Screening	-28 to -14	<-14	<-14		<-14
Baseline	1	-14 - 1	-14 - 1		-14 - 1
Week 2	15	2 - 21	2 - 21		2 - 21

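### The 14-day on-treatment cut-off leaves no room for the ±3-day visit windows, so compliant closing visits can drop out of the by-visit safety summaries that SAP Table 12 would keep them in

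*SAP*

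**What the plan says.** **The period.** SAP 2.1 ends the Period A on-treatment period by one of two dates, taking the earlier: "to the last blinded administration of the IMP + 14 days, or the first open-label IMP administration, whichever occurs earlier". For Period B it is "the period from the first open-label IMP administration to the last open-label administration of the IMP + 14 days".

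**Its use.** SAP 2.7.3.1 says that, for laboratory, vital-sign and ECG variables, "descriptive statistics for results and changes from baseline will be provided for each analysis window during the on-treatment period". Protocol 9.2.6.2 has the same restriction, "for each planned visit during the on-treatment period".

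**The schedule.** Blinded treatment is SAR442970 or "matching placebo Q2W at the Week 0 visit up to the Week 14 visit as part of Period A" (SAP 1.1), and the last open-label dose is at Week 26. The Protocol 1.3.1 schedule puts Weeks 14, 16, 26 and 28 on Days 99, 113, 183 and 197, each ±3 days. A footnote there counts the visit dates from the first dose, not from the previous one. US non-responders have their end-of-treatment visit at Week 20 (Day 141 ±3) without a dose, so their last dose is at Week 18 (Day 127 ±3).

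**The windows.** SAP Appendix 4 says that the analysis windows decide how visits enter the by-visit analyses, and that an available measurement inside its window is used. In Table 12 the Week 16 window runs from Day 106, and its footnote says "Last window in Period A is the 1st dose of open-label IMP administration". Week 28 runs from Period B Day 78 to 112, and Week 36 is everything after Day 112.

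**The concern.** The cut-off equals the planned interval between the last dose and the closing visit, so there is no slack at all. A participant who meets both visit windows can still have the Week 16, Week 28 or US Week 20 end-of-treatment values classed as residual-treatment values and left out of the by-visit tables. Table 12 and Appendix 4 point the other way. Two programmers working from the same SAP could therefore produce different tables.

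The affected visits are not minor ones. Week 16 is the last placebo-controlled assessment and Week 28 closes treatment. A Week 16 value excluded from Period A is not recovered in Period B, because the first Period B window in Table 12 opens on Day 2. The number summarised would fall at these visits for a reason unrelated to safety or compliance.

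**Working it through.** The plan gives no figure for this loss, so there is none to reproduce. The check is day arithmetic.

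**1. Planned gap.** 113 − 99 = 14; 197 − 183 = 14; 141 − 127 = 14. Each equals the cut-off.

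**2. Gap allowed by the protocol.** Let *a* be the offset of the last dose and *b* the offset of the closing visit, each from −3 to +3 days. Then gap = 14 + *b* − *a*, with minimum 14 − 6 = 8 and maximum 14 + 6 = 20.

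**3. Exact condition.** The visit is excluded when gap > 14, that is when *b* > *a*. Lateness alone does not decide it:

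| Closing visit | Offset pairs | Excluded |
|---|---|---|
| 1 to 3 days late | 21 | 4 + 5 + 6 = 15 |
| On the day | 7 | 3 |
| 1 to 3 days early | 21 | 2 + 1 + 0 = 3 |
| All | 49 | 21 |

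Six of the 21 late-visit pairs stay in because the last dose was equally late or later. An on-time visit is excluded if the last dose was early.

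**4. Share lost.** The documents give no distribution of visit timing, so these are assumptions. Suppose *a* and *b* are independent, a fraction *q* of visits is exactly on day, and the rest is spread evenly over the other six offsets. Then P(*b* > *a*) = [1 − *q*² − (1 − *q*)²/6] / 2.

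| *q* | Share lost |
|---|---|
| 1/7 (uniform) | 21/49 = 0.429 |
| 0.50 | (1 − 0.250 − 0.0417)/2 = 0.354 |
| 0.70 | (1 − 0.490 − 0.0150)/2 = 0.248 |
| 0.90 | (1 − 0.810 − 0.0017)/2 = 0.094 |

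If late visits tend to follow late doses, the share is lower. It is zero if the two offsets are always equal.

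**5. The first open-label dose does not rescue the value.** SAP 2.1 takes the earlier date, and with a gap above 14 days that is last dose + 14.

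**6. Protocol and SAP differ at Week 16.** Protocol 9.2.1 defines one on-treatment period up to the last dose of any IMP + 14 days. On that wording, the Week 16 value of a participant who goes on to open-label dosing lies inside it. The Week 16 loss comes from the SAP's split by period; the Week 28 and US Week 20 losses arise under both documents.

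**7. The Week 36 window.** Counted from the first open-label dose, the last dose falls on Period B Day 183 − 113 + 1 = 71, ±6, so Day 65 to 77. On-treatment then ends on Day 79 to 91. The Week 36 window opens after Day 112, so an on-treatment restriction leaves it empty on this schedule.

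**8. Would 20 days be clean?** It covers the largest compliant gap in step 2. The visit after that is planned 28 days after the last dose, with a compliant range of 22 to 34 days. A 20-day cut-off therefore admits the closing visit and no later scheduled one.

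**The case against.** The strongest reply is that this is a conflict between two rules, not a demonstrated loss. Appendix 4 says that the windows govern by-visit use, and a Week 36 window makes little sense if the tables stop at last dose + 14 days. The sponsor may well have meant to keep the late values. That stands as evidence of intent, but SAP 2.7.3.1 states the restriction in terms and nothing says which rule prevails.

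The second reply concerns weight, and it stands. Safety analysis is descriptive with no testing. Adverse-event and PCSA incidence use the treatment-emergent period, which in Period A extends to 75 days after the last blinded dose or to the first open-label dose if earlier, so a late pre-dose Week 16 value still counts there. Efficacy is not tied to the on-treatment period. The blinded arms share one schedule, so there is no evident reason for bias between them.

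Four stronger readings are tempting and not supported:
- That every late visit drops out. Only a gap above 14 days matters.
- That 43% of Week 16 data will be lost, with standard errors about 1.3 times wider. This takes the top of an assumed range.
- That Week 16 ECGs are lost. The flowcharts, as they can be read here, mark that ECG under Week 18, possibly through a column shift.
- That the remedy is to use every Table 12 value. Protocol 7.1.1 asks participants who stop IMP to stay for assessments where possible, so this would bring off-drug values into on-treatment tables.

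**Conclusion.** The concern holds as a minor one. As written, SAP 2.1 with 2.7.3.1 excludes any closing visit more than 14 days after the last dose from the by-visit quantitative safety summaries, while the protocol allows up to 20 days and Table 12 would keep the value. This applies at Week 16, Week 28 and the US Week 20 end-of-treatment visit.

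The day arithmetic rests only on the documents. The size does not: about 9% to 43% under independent offsets, less with positive dependence, and unknown in this trial. The effect is confined to descriptive laboratory and vital-sign summaries by visit, and ECG where scheduled. No safety endpoint, estimand or efficacy result changes.

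**What to change.** For the by-visit quantitative safety summaries only, amend the SAP to say:

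- The on-treatment cut-off is the last dose + 20 days (14 days plus the 6-day cumulative visit tolerance). In Period A it is capped at the first open-label dose, with pre-dose values on that day included.
- Table 12 windows apply within that period, so later values from participants who stopped IMP early stay excluded.
- How the Week 36 window is summarised. It needs its own rule, because even a 20-day cut-off ends on Period B Day 85 to 97.

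Align Protocol 9.2.1 and 9.2.6.2, or list the change in SAP 2.10.

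The cost is a short text change before database lock and no new data. The downside is that values up to 6 days beyond the dosing interval count as on-treatment in these tables. A participant who misses the Week 14 dose but continues would still be excluded at Week 16, since that gap is at least 22 days; the SAP should say that this is intended.

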*bb* Hidradenitis Suppurativa Clinical Parameters will be performed at each designated study visit and must address all relevant anatomical regions in each participant; the number, location, longest distance between relevant lesions, and whether the lesions are separated by normal-appearing skin will be measured in each anatomical area ; Hurley Stage is included as an assessment performed during the HS clinical parameters; Hidradenitis Suppurativa Physician's Global Assessment is included as an assessment performed during the HS clinical parameters. The site is responsible for counting lesions that received intervention as permanently present in the lesion counts from the date of the intervention. The data collected from the HS clinical parameters will be used for the derivation of the HiSCR50, HiSCR75, HiSCR90, IHS4, AN count, Hidradenitis Suppurative Physician's Global Assessment, raw counts, and disease flares. For each participant it is recommended that the HS Clinical Parameters is assessed by the same Investigator during the entire study if possible.

*cc* Investigator review of participant daily analgesic use diary.

*dd* The participant should complete the questionnaire before site personnel perform any clinic assessments and before any interaction with the site personnel has occurred to avoid biasing the participant's response.

*ee* Number of samples (tubes) and quantity of biological samples needed for each assessment can be found in the laboratory manual.

*ff* Up to 4 hours prior to IMP administration.

*gg* PD biomarkers will include serum TNF and serum OX40L.

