### **Lesion Intervention**

In the event that an acutely painful lesion occurs that requires an immediate intervention, Investigators will have the option to perform protocol-allowed interventions.

Only 2 types of interventions are allowed: injection with intralesional triamcinolone acetonide suspension (at a concentration of up to 10 mg/mL, up to 1 mL) and I&D.

For participants in Chile, intralesional betamethasone (at a maximum dose of up to 1.5 mg, diluted in sterile normal saline per Investigator discretion) may be substituted for intralesional triamcinolone.

New systemic and topical therapies following I&D (including antibiotics), are prohibited.

Participants should continue using any ongoing oral and topical therapies (with the constraints as described in [Section 6.9.1](#)) during the study. Concomitant medications associated with the lesion intervention(s) must be captured in the source and on the appropriate eCRF.

Protocol-allowed interventions are prohibited during Period A for all participants except those in Australia. For participants in Australia, 2 lesion interventions are allowed during Period A. An intervention can occur on two different lesions at the same visit or on the same lesion at two different study visits.

During Period B, maximally two interventions every 4 weeks are permitted. An intervention can occur on two different lesions at the same visit or on the same lesion at two different study visits.

All study visit assessments must occur before any interventions are performed. The site will be required to count any lesion that undergoes an intervention as permanently present from the date of the intervention and must account for it in the source document(s) and on the appropriate eCRF.

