## 9.4 TIMING OF STATISTICAL ANALYSES

A primary database lock and an early analysis will be performed when the last participant (biologic and small molecule immunosuppressive-naïve and TNF-experienced) completes 16 weeks treatment duration (ie, complete study primary endpoint assessment). The analysis of the primary endpoint performed during the early analysis will be the final analysis of the primary endpoint.

Final analysis will be performed when all participants will have reached EOS Visit.

The SAP will describe the planned early analysis in greater detail.

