2.2 PRIMARY ENDPOINT(S) ANALYSIS

2.2.1 Definition of endpoint(s)

The primary endpoint is the percentage of biologic and small molecule immunosuppressive-naïve participants achieving HiSCR50 at Week 16. It is defined as $\geq 50\%$ reduction from Baseline in the total abscess and inflammatory nodule (AN) count, with no increase from Baseline in abscess or draining tunnel count.

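### SAP 2.1 counts a locally treated lesion as present with no start date, contradicting the protocol; applied literally, it would let Period B interventions change Week 16 HiSCR50 status

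*SAP*

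**What the plan says.** **Counting rule, SAP.** At the end of section 2.1, for a lesion treated by steroid injection, deroofing or another local procedure, "the lesion is considered present throughout the double-blind period and open-label period". The lesion types listed include abscesses, inflammatory nodules and draining tunnels, which are the components of HiSCR and IHS4.

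**Counting rule, protocol.** Under Lesion Intervention in section 6.9.2, the site must "count any lesion that undergoes an intervention as permanently present from the date of the intervention". Footnote bb of the schedule in section 1.3.1 makes the site responsible for "counting lesions that received intervention as permanently present in the lesion counts from the date of the intervention"; footnote cc of the US schedule in section 1.3.2 says the same.

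**When interventions may occur.** "Protocol-allowed interventions are prohibited during Period A for all participants except those in Australia"; Australian participants may have two in Period A. After that, "During Period B, maximally two interventions every 4 weeks are permitted".

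**Endpoint.** HiSCR50 in SAP 2.2.1 has two parts: the AN count must fall to half its baseline value or lower, and this must come "with no increase from Baseline in abscess or draining tunnel count".

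**Timing.** Protocol 9.4 locks the data when the last participant completes 16 weeks, and "The analysis of the primary endpoint performed during the early analysis will be the final analysis of the primary endpoint".

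**Declared changes.** SAP section 1 reports no major departure from the protocol's analyses. Table 9 in SAP 2.10 lists only a DLQI threshold.

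**The concern.** The two rules differ in where the count starts. The protocol's rule runs forward from the procedure. The SAP's rule, as worded, covers the whole double-blind period whatever the date of the procedure. For a lesion that did not exist until Period B, it puts a lesion into Week 16 and earlier post-baseline counts that no assessor saw there.

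If the sentence were programmed that way, a blinded, placebo-controlled Week 16 comparison would depend on events after Week 16, when both arms receive SAR442970 and everyone knows it. It would also depend on enrolment date. At the Week 16 lock the earliest participants could have up to 12 weeks of Period B follow-up on file and the last almost none, so two people with identical Week 16 examinations could be classified differently. The other Week 16 endpoints built on the same counts (HiSCR75, HiSCR90, the IHS4 endpoints and flare) and the time to first HiSCR50 would be exposed too.

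**Working it through.** The plan gives no figure for this point. Its stated precision for the primary comparison (80% credible interval half-width below 0.145 with 66 participants, protocol 9.5) does not depend on the counting rule. With 44 versus 22 participants, the Beta(2.1, 4.9) placebo prior, an assumed placebo rate of 0.30, assumed SAR442970 rates of 0.45 to 0.65 and vague priors on that arm, it recomputes to 0.140 to 0.144. It stands whichever rule is used.

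**1. Which counts the literal rule reaches.** SAP 2.1 defines baseline as the last value before the first double-blind dose. Baseline therefore lies outside both periods named in the sentence and stays fixed. Every post-baseline count up to Week 16 lies inside.

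**2. What one added lesion does to HiSCR50.** Reduction = (baseline AN − Week 16 AN) / baseline AN.

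| Baseline AN | Week 16 AN as recorded | Reduction | After adding one nodule | Reduction |
|---|---|---|---|---|
| 6 | 3 | 3/6 = 50%, responder | 4 | 2/6 = 33%, non-responder |
| 3 (minimum for entry) | 1 | 2/3 = 67%, responder | 2 | 1/3 = 33%, non-responder |

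The abscess condition can fail even when the AN condition holds by a wide margin. With baseline AN 10 and Week 16 AN 1, and no abscess at either, the reduction is 90%. One abscess first treated in Period B gives AN 2 (80%), but the abscess count is now 1 against 0 at baseline: non-responder.

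**3. How many added nodules are needed.** For baseline AN b and Week 16 AN w, the number is floor(b/2) − w + 1. It is 1 for 6 to 3, but 5 − 2 + 1 = 4 for 10 to 2. Participants well past the threshold are robust on the AN condition.

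**4. The most that Period B allows.** Two interventions per 4 weeks over 12 weeks gives 2 × 3 = 6. These need not be six lesions, because protocol 6.9.2 lets the same lesion be treated at two visits. US participants who do not respond at Week 20 leave Period B early. A lesion already present and counted at Week 16 adds nothing.

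**5. Other Week 16 endpoints.** Baseline AN 10 and Week 16 AN 2 meets HiSCR75 (80%); AN 3 does not (70%). Baseline AN 6 and Week 16 AN 7 is not a flare (an increase of 1); AN 8 is (an increase of 2, 33%).

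**6. Effect on the treatment difference, illustration only.** The response rates (55% versus 30%) and the fractions of responders reclassified are all assumed.

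| Reclassified, SAR442970 / placebo | Response rates | Difference (points) |
|---|---|---|
| 0% / 0% | 55.0% vs 30.0% | 25.0 |
| 5% / 5% | 52.25% vs 28.5% | 23.75 |
| 10% / 10% | 49.5% vs 27.0% | 22.5 |
| 20% / 20% | 44.0% vs 24.0% | 20.0 |
| 15% / 5% | 46.75% vs 28.5% | 18.25 |
| 5% / 15% | 52.25% vs 25.5% | 26.75 |

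**7. Under the protocol rule.** A Period B procedure changes no count dated before it. Every example in step 2 remains a responder.

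**The case against.** The strongest reply is that the sentence is loosely drafted carry-forward: once treated, a lesion stays in the count and does not drop out when Period A ends. Much supports this. The protocol states the forward rule three times, and the SAP says that it follows the protocol. Sites apply the rule as they count, and protocol 8.2.1.2 calculates HiSCR from the counts recorded in the eCRF. SAP Table 13 closes the Week 16 window for HS clinical parameters at the first open-label dose. The SAP describes no step for adding lesions to earlier visits or for matching a Period B lesion to a Week 16 count. If HiSCR comes only from those eCRF counts, no Week 16 status changes.

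All of that stands, and it makes the harm conditional. It does not make the sentence right. If the site counts govern, the sentence is redundant and misstates the rule; if it is programmed, it gives wrong counts. The SAP does not say which. Nor does the sentence simply restate protocol 6.9.2, since it covers deroofing, which protocol 6.9.1 prohibits. The wording also matters because Table 5 marks intralesional corticosteroids for treatment-policy handling in the HiSCR endpoints, so for them the lesion count carries the effect.

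A reader might infer more than the documents support:

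- That the SAP establishes a back-dating algorithm, so that the primary result will be wrong. It contains one sentence that can be read that way and no procedure that carries it out.
- That most treated lesions will be Period B lesions. The permissions make this plausible, but no intervention rate is given for either period.
- That the error would favour one arm. The documents give no basis for a direction, and under protocol 6.4 sites are not told Period A allocation until the study ends.

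**Conclusion.** The point holds as a wrong stated rule, not merely a missing detail. SAP 2.1 contradicts protocol 6.9.2 and both schedule footnotes on when a treated lesion starts to count, and the difference is undeclared. The consequence depends on programming. Applied literally, one lesion that is new after Week 16 and treated in Period B is enough to reverse HiSCR50 for a participant at the 50% threshold, or for one whose Week 16 abscess or draining tunnel count equals baseline if the lesion is of that type. Status at the Week 16 lock would then vary with the length of Period B follow-up. If the eCRF counts are used as recorded under the protocol rule, the effect is nil. The number of participants affected lies somewhere between none and an unknown figure, and the shifts in the illustration rest wholly on assumed rates. The sentence should be corrected before the primary endpoint is derived, because it bears directly on that derivation.

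**What to change.** Replace the treated-lesion sentence in SAP 2.1 with the protocol rule:

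- A lesion that receives a local intervention is counted as present at assessments from the date of that intervention onward.
- Counts before that date stay as recorded.
- Interventions after the Week 16 assessment cannot affect Week 16 or earlier endpoints.

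If the SAP is also to fix the lesion type under which a treated lesion is carried forward, label that as a SAP clarification, since the protocol does not state it. It would help to add that HiSCR and IHS4 are derived from the eCRF counts without further adjustment, if that is the intention.

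One neighbouring conflict affects same-day counts. The order-of-assessment footnotes in both schedules (a in section 1.3.1, b in section 1.3.2) list lesion intervention before the HS clinical parameters, whereas protocol 6.9.2 puts all visit assessments before any intervention. These passages must be reconciled.

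The cost is a few sentences in the SAP and a check of the derivation program. No new data, no change to sample size and no change to the stated precision follow.
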